Detailed data will be collected on consecutive patients with acute TBI (see: *Planned inclusion/exclusion criteria*). However, administrative and CCMDS data will be collected for all admissions to all participating units. Critical care data on TBI patients will be placed in the context of all TBI, including those not admitted to critical care, using data from the Trauma Audit & Research Network (TARN).

Data collected will cover administrative (e.g. NHS Number, dates and times) and socio-demographic factors and factors from pre-hospital, and the first and subsequent hospitals as well as factors at arrival to the definitive location for neurocritical care. Data items collected will include all those required to calculate the models selected from Phase I, including: mechanism, severity and timing of TBI and other injuries; CT scan classification (first/last prior to admission); components of and total GCS (pre-intubation/at admission); pupil reactions (first/worst); and physiological parameters (first/worst).

The experience from the CRASH trial suggests that adequate quality CT data can be obtained through reports generated at contributing centres, and this will be our

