primary method by which imaging data will be recorded. However, we are aware that there have been concerns expressed in the past about the validity of such peripheral reporting in clinical trials. It is essential to know whether the data obtained from local reporting of CT images is adequate for accurate risk adjustment, since this will have significant implications on the practicability of using any particular predictive model. Data collectors will therefore be asked to record appropriate identifiers to allow us to access CT scans for review at a later date if required, and will be requested not to discard or destroy the films or digital imaging data for these patients until 5 years after entry into the study. We will obtain copies of the admission CT scans in a randomly selected sample of 10% of patients, weighted to include more patients from outside neuroscience centres, where patient throughput will be lower. Data collectors will be requested to send anonymised admission CT scans to Addenbrookes Hospital (Cambridge University Hospitals NHS Foundation Trust) using the Image Exchange Portal, where possible. These will be centrally viewed and assessed by Neurosciences Critical Care Consultants at Addenbrookes Hospital, and the reports generated will be compared to the corresponding submitted data to identify any systematic discrepancies. If significant discrepancies are identified, we will arrange systematic collection and central reporting of CT scans from all patients, subject to additional funding.

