The risk prediction models selected in Phase I will be calculated from the raw data collected in Phase II using standardised computer algorithms. Any ambiguities in the precise methods for each model will be clarified by contacting the model authors.

Models will be validated with measures of discrimination (the ability to separate survivors from non-survivors or those with favourable outcomes from those with unfavourable outcomes), calibration (the degree of agreement between the observed and predicted outcomes) and overall goodness-of-fit. If the calibration is poor, then the best model(s) will be recalibrated to provide revised coefficients specific to UK neurocritical care.

Assessment of loss to follow-up

Available data from the critical care and hospital stay will be used to compare the characteristics of responders and non-responders and to determine whether response varies by: age; severity of injury; physiological response to injury; organ monitoring

and support received in critical care; duration of stay in critical care and in hospital; destination following discharge from acute hospital; and predicted 6-month outcome.

Provided all variables associated with missing response are included in the risk model, complete case analysis of data with missing responses is statistically valid, under the assumption that data are missing at random given the observed covariates. We therefore do not propose using statistical methods for missing data such as multiple imputation unless: (1) the observed loss to follow up is considerably higher than anticipated; or (2) factors relating to processes of care (e.g. duration of critical care stay), and therefore excluded from the risk models, are found to be independent predictors of missing response.

Validation methods

Risk prediction models will be validated for discrimination, calibration and goodness-of-fit, based on methods used previously for the validation of risk prediction models for adult, general critical care^{4;5} and paediatric critical care,²⁷ and for evaluating general risk prediction models in patients with TBI.⁶

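### The CT re-read looks for systematic discrepancies between reports, not for the effect of local CT reading on predicted risk by unit type, and does not say which recorded scan is re-read

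*Protocol*

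**What the plan says.** The relevant text is in the protocol, under Phase II: Data collection and data validation.

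- **Purpose:** "It is essential to know whether the data obtained from local reporting of CT images is adequate for accurate risk adjustment". The protocol adds that the answer bears on whether a given model can be used in practice.
- **Data recorded locally:** the items listed include "CT scan classification (first/last prior to admission".
- **Scans re-read:** "We will obtain copies of the admission CT scans in a randomly selected sample of 10% of patients". The sample is "weighted to include more patients from outside neuroscience centres, where patient throughput will be lower".
- **Comparison:** "the reports generated will be compared to the corresponding submitted data to identify any systematic discrepancies".
- **Consequence:** "If significant discrepancies are identified, we will arrange systematic collection and central reporting of CT scans from all patients, subject to additional funding".

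Two later sections matter. Under Phase III the models "will be calculated from the raw data collected in Phase II using standardised computer algorithms". Under Phase IV the effect of unit type and location on six-month outcome is estimated in multilevel logistic models that adjust for the selected risk model.

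**The concern.** The question is about risk adjustment, so it belongs on the scale of predicted risk and has to be asked of each model. The stated criterion is about reports: do central and local readings differ systematically? The two can come apart. Balanced errors produce no systematic difference but weaken a model. Conversely, a systematic difference in an item with little weight may hardly move predicted risk.

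Three things are at stake.

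- **Phase III.** Loss of discrimination from misreading falls only on models with CT terms. The Background describes CT versions of the CRASH models and the IMPACT extended and lab models, alongside CRASH basic and IMPACT core without CT. Validation on local data will include that loss, but nothing stated would attribute it to reading.
- **Phase IV.** If a CT-containing model is selected and reading quality differs by unit type, the error in the adjustment is aligned with the exposure being compared. No comparison of readings by unit type is stated.
- **The re-read itself.** If the scan sent to the central readers is not the one behind the submitted classification, change in the lesion between scans can be counted as disagreement between readers.

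**Working it through.** **1. Size of the re-read.** Inputs are from Proposed sample size.

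- Inflation for loss to follow-up: 3,100 / (1 − 0.08) = 3,370, which the protocol rounds up to 3,400.
- Accrual: 18 × (12×8 + 13×6 + 30×0.5) = 1,728 + 1,404 + 270 = 3,402, in agreement.
- 10% of 3,400 = 340 patients. The protocol gives no precision or threshold for the re-read.

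**2. What the over-sampling achieves.** Units outside neuroscience centres supply 270 / 3,402 = 7.9% of patients, so proportional sampling would give 340 × 0.079 ≈ 27 of their scans. The 95% half-width is 1.96 × √(p(1−p)/n). With an assumed discrepancy rate of 10% and n = 27 it is 11.3 points. With an assumed 15% it is 13.5 points at n = 27, 7.6 at n = 85 (a quarter of the sample) and 5.4 at n = 170 (half). The sampling weight is not stated, so these shares are assumptions. The weighting is what makes a report by unit type feasible.

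**3. Can misreading matter without a systematic discrepancy?** The yardstick is the 0.03 difference in c index (0.83 versus 0.80) in Appendix 3. Simulating that comparison (binormal scores, 40% events, DeLong test, two-sided 0.05) gave 79.2% power at 3,100 with uncorrelated scores, so 0.03 is the difference behind the sample size.

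The illustrative model is an assumption: log odds = −1 + x + 1×CT, with x normal (mean 0, SD 1.25) and the CT finding present in 40%. It gives 39% unfavourable outcomes, against 40% in the protocol. A fraction e of patients is misread, half as false positives and half as false negatives. Then:

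- net change in recorded prevalence = e/2 − e/2 = 0;
- mean change in predicted log odds = (e/2)(+1) + (e/2)(−1) = 0;
- SD of that change = √e.

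| Misread (e) | Mean change, log odds | SD, log odds | c index | Loss | Loss / 0.03 |
|---|---|---|---|---|---|
| 0 | – | – | 0.7941 | – | – |
| 5% | 0 | 0.22 | 0.7896 | 0.0045 | 15% |
| 10% | 0 | 0.32 | 0.7848 | 0.0093 | 31% |
| 20% | 0 | 0.45 | 0.7762 | 0.0179 | 60% |

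A search for systematic discrepancies sees the zeros. The spread of the change shows the problem, so a mean alone would not be enough either.

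**4. Which scan?** The recorded fields are the first and the last CT before admission; the request is for the admission CT. The section on delivery of neurocritical care says patients pass through several services, and Phase II collects data from the first and later hospitals, so serial scans are foreseeable. If admission CT means the last scan, the first-scan field goes unchecked. If it means the first, the last goes unchecked. If it means a scan done on arrival at the unit, it may match neither.

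**5. Route into the location result.** The selected risk model is the patient-level adjustment, and unit type and location are the factors of interest. CT error that differs by unit type therefore enters the location effect directly. The protocol gives no CT error rates, so this bias is not sized here.

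**The case against.** The strongest reply is that this is detail for the SAP, which is not at hand. Both readings will exist for every sampled patient, the Phase III algorithms can compute risk from either, and the Steering Group approves the SAP (Appendix 4). That stands in part: nothing prevents the better analysis. But the protocol does not simply leave the measure open. It names a criterion, ties the decision to it, and tells sites which image to send. A SAP cannot put right an image request that has already been carried out.

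Several stronger readings are tempting, but the text does not support them.

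- *The check cannot show adequacy.* Too strong. The data to be collected would allow it; the stated comparison does not do it.
- *The scans are not matched to the recorded data.* The protocol compares with the corresponding submitted data, which implies an intended match, and Phase I leaves precise definitions to a data collection manual. What remains is that the admission scan is not tied to either field.
- *Over-sampling outside units distorts the result.* The weighting is deliberate and explained, and step 2 shows its value. Only a crude pooled rate would be distorted, and the protocol names no such rate. It does not say that items are compared one by one or that one overall figure decides.
- *A failed check would change nothing.* Model selection in Phase III also weighs each model's strengths, weaknesses and ease of data collection, so poor CT data could steer the choice without new funding. What remains is that the one stated response depends on funding, with no fallback for the location result.

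It is also fair that no CT-containing model has yet been chosen. The Phase IV part of the concern is conditional on that.

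**Conclusion.** The concern holds in limited form. As written, the re-read does not measure what the protocol says it needs to know. It does not show how far predicted risk moves, it could miss non-systematic misreading, and it states no comparison by unit type. The scan to be re-read is not identified precisely enough.

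The illustrated loss of c index is 0.0045 to 0.018 for 5% to 20% balanced misreading, or 15% to 60% of the difference used for sample size. This rests on an assumed model (one CT finding, 40% prevalence, log odds ratio 1) and assumed misreading rates. It shows that the gap can matter, not that local reading is poor. The Phase IV bias needs two further conditions: a CT-containing model is selected, and reading differs by unit type.

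**What to change.** 1. State that the scan re-read is the one from which the submitted classification used by the models was made. If models use both the first and the last scan, request both.
2. In the re-read patients, compute each CT-containing model twice, with local and with central CT readings. Report the mean and the spread of the change in predicted risk separately for the three unit types, plus an overall figure weighted by inverse sampling probability.
3. Define significant discrepancies in terms of that change, including a difference between unit types.
4. If central reading of all scans is not funded, show the location result with a non-CT model (for example IMPACT core or CRASH basic) alongside the main one.

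Keep the over-sampling of outside units. A c index or calibration by unit type in the re-read sample is not proposed: if 68 outside patients were sampled, 40% with an unfavourable outcome gives 68 × 0.40 ≈ 27 events before loss to follow-up, too few to be useful.

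The cost is some wording, a modest extra analysis on the same 10% of patients with the same readers, and possibly a second scan to read for some transferred patients.

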The risk prediction models selected in Phase I will be calculated from the raw data collected in Phase II using standardised computer algorithms. Any ambiguities in the precise methods for each model will be clarified by contacting the model authors.

Models will be validated with measures of discrimination (the ability to separate survivors from non-survivors or those with favourable outcomes from those with unfavourable outcomes), calibration (the degree of agreement between the observed and predicted outcomes) and overall goodness-of-fit. If the calibration is poor, then the best model(s) will be recalibrated to provide revised coefficients specific to UK neurocritical care.

Assessment of loss to follow-up

Available data from the critical care and hospital stay will be used to compare the characteristics of responders and non-responders and to determine whether response varies by: age; severity of injury; physiological response to injury; organ monitoring

and support received in critical care; duration of stay in critical care and in hospital; destination following discharge from acute hospital; and predicted 6-month outcome.

Provided all variables associated with missing response are included in the risk model, complete case analysis of data with missing responses is statistically valid, under the assumption that data are missing at random given the observed covariates. We therefore do not propose using statistical methods for missing data such as multiple imputation unless: (1) the observed loss to follow up is considerably higher than anticipated; or (2) factors relating to processes of care (e.g. duration of critical care stay), and therefore excluded from the risk models, are found to be independent predictors of missing response.

Validation methods

Risk prediction models will be validated for discrimination, calibration and goodness-of-fit, based on methods used previously for the validation of risk prediction models for adult, general critical care^{4;5} and paediatric critical care,²⁷ and for evaluating general risk prediction models in patients with TBI.⁶

Discrimination will be assessed by the concordance (or *c* index),²⁸ equivalent to the area under the ROC curve.²⁹ The *c* index can be interpreted as the probability that a randomly selected patient with an unfavourable outcome will have a higher risk prediction than a randomly selected patient with a favourable outcome. The *c* index will be compared between different models (for the same outcome) using the non-parametric method of DeLong, DeLong and Clarke-Pearson.³⁰

Calibration will be assessed graphically by dividing the patients into ten groups at the deciles of the predicted risk and plotting the observed outcome against the expected outcome in these groups. The Hosmer-Lemeshow test will be used to test the hypothesis of perfect calibration,³¹ however we note that this test is highly sensitive to sample size³² and so a significant test result alone will not be taken to indicate 'poor' calibration. In addition, Cox's calibration regression will be used to relate the observed to the predicted outcomes.³³ Cox's calibration regression fits the model *true log odds* = α + β *predicted log odds* using logistic regression. If the model is perfectly calibrated, then $\alpha = 0$ and $\beta = 1$, i.e. *true log odds* = *predicted log odds*.

Overall model fit will be assessed with Brier's score,³⁴ the mean squared error between the observed and predicted outcomes.

Selection of optimum model(s)

The strengths and weaknesses of each model will be assessed, including consideration of factors such as the purpose(s) for which each model is suited, the choice of outcome variable, and the ease of data collection in addition to statistical performance.

Phase IV: Evaluation of location of neurocritical care

The existence of a validated risk prediction model for patients with TBI admitted to critical care will enable both non-randomised, observational research and audit in neurocritical care. The first research question that we aim to address using this model, forming part of this proposal, is:

“What is the clinical- and cost-effectiveness of managing of TBI in a dedicated neurocritical care unit within a neurosciences centre compared with a general critical care unit within a neurosciences centre or a general critical care unit not in a neurosciences centre?”

The cost analysis will take a health and personal social services perspective.³⁵ For each admission, each day during the hospital stay will be assigned to the appropriate healthcare resource group (HRG) using daily organ support data recorded for the CCMDs. For each admission, the costs per hospital bed-day for each HRG during critical care and for each bed-day for general medical care will be taken from the Payment by Results database using trust-specific unit costs.³⁶ These unit costs will be combined with each patient's resource use data to estimate the total cost of each initial hospital admission. Information will be collected on hospital readmissions and use of community health services post discharge at six-month follow-up. The study will report the total six-month hospital and community health service costs for each case. The analysis will compare mean costs across the groups recognising any differences in either the resource use or unit costs.

The effect of location of neurocritical care on six-month mortality and unfavourable outcomes will be evaluated using multilevel logistic regression models. Using a

multilevel model (MLM) enables adjustment for both patient-level factors, including the selected risk prediction model, and unit-level factors, such as the volume of cases, the size of the unit and, most importantly, the type (specialist or general) and location (neuroscience centre or not) of the unit.

The cost-effectiveness analysis will use the six-month EQ-5D, health services questionnaire and survival data to report six-month QALYs (risk adjusted). These endpoints will be valued at different levels of willingness to pay for a QALY gain to report risk-adjusted incremental net benefits of each location of neurocritical care. The cost and cost-effectiveness analysis will also use MLMs^{37;38} to report risk-adjusted incremental costs and cost-effectiveness according to the unit type and location. The bivariate cost-effectiveness models will recognise the correlation between costs and outcomes. The MLMs will also acknowledge the notoriously skewed nature of cost data by allowing the individual error terms to have non-normal distributions (e.g. gamma or log-normal). Finally, a cost-effectiveness model will extrapolate from the risk-adjusted estimates of six-month cost and outcomes to project risk-adjusted cost-effectiveness over the lifetime. An extensive sensitivity analysis will investigate whether the conclusions about the relative cost-effectiveness of care delivery are robust to assumptions made about model specification

Planned inclusion/exclusion criteria

All adult patients (aged 16 years or over) admitted to participating critical care units following TBI, and with a GCS<15 following resuscitation, will be identified by the treating clinicians. Confirmation reports will be sent to all units to ensure that every eligible admission is identified and, where possible, data will be validated against the Case Mix Programme database and CCMDS returns.

Any patient initially thought to have TBI, and entered into the RAIN database, but subsequently found to have a different cause for their neurological impairment (e.g. cerebrovascular accident) will be excluded from analyses.

When evaluating each risk prediction model, additional exclusion criteria will be applied to match the definitions of the population used to develop the model. For example, any model derived on only patients with severe head injury (GCS≤8) or

moderate to severe head injury (GCS \leq 12) would be validated on the equivalent population.

Planned interventions

None.

Proposed outcome measures

The primary outcomes will be mortality and unfavourable outcome, defined as death, vegetative state or severe disability on Glasgow Outcome Scale (Extended), at six months following admission to critical care. The duration of follow-up has been restricted to six months for the purpose of this study as this is the primary endpoint of the existing risk prediction models, and to limit costs, however discussions with service user representatives indicate that longer-term outcomes may be important. Further list cleaning against the NHS Central Register will enable ongoing follow-up of mortality beyond six months. Secondary outcome measures will include six-month and lifetime costs and cost-effectiveness.

Proposed sample size

We performed a simulation study to assess the power to detect a difference in the c index (area under the receiver operating characteristic, ROC, curve) between two different risk prediction models applied to the same population. Simulations were based on the following assumptions: the rate of unfavourable outcomes in the population will be 40% (based on the observed rate of unfavourable outcomes in high income countries in the CRASH trial,¹¹ and consistent with the results of a regional audit in East Anglia³⁹); statistical tests will be based on a two-sided p-value of $P=0.05$; we wish to be able to detect, with 80% power, a 10% relative difference in c index from the value of 0.83 observed for the CRASH model in the development sample.¹¹ A total of 17,500 datasets were simulated at different sample sizes using a binormal model⁴⁰ and the empirical power was assessed at each sample size as the proportion of datasets in which a statistically significant difference was detected (see Appendix 3).

Based on these simulations, a sample size of 3100 patients will be required for model validation. To allow for 8% loss to follow-up (based on the observed follow-up rates from CRASH and RESCUEicp), we will aim to recruit 3400 patients.

Using data from the Case Mix Programme Database, we anticipate the rate of admission of patients with TBI to be approximately 8 per unit per month for neurocritical care units, 6 per unit per month for general critical care units within a neuroscience centre, and 0.5 per unit per month for general critical care units outside a neuroscience centre. We will therefore aim to recruit at least 12 neurocritical care units, 13 general critical care units within neuroscience centres and 30 general critical care units outside neuroscience centres to complete recruitment within 18 months.

ORGANISATION

Study Steering Group

The Study Steering Group (SSG) responsibilities are to approve the study protocol and any amendments, to monitor and supervise the study towards its research objectives, to review relevant information from external sources, and to resolve problems identified by the Study Management Group. Face-to-face meetings will be held at regular intervals determined by need and not less than once a year, with routine business conducted by telephone, email and post. The SSG membership is shown below and terms of reference are given in Appendix 4. Representatives of the funder (NIHR HTA Programme) and the sponsor (ICNARC) will be invited to observe at SSG meetings.

Membership

[name] (Independent Chair)	Director, Centre for Anaesthesia UCL
[name] (Chief Investigator)	Statistician, Intensive Care National Audit & Research Centre (ICNARC)
[name] (Co-investigator)	Lecturer in Health Economics, London School of Hygiene and Tropical Medicine
[name] (Co-investigator)	Senior Surgical Scientist, Academic Neurosurgery Unit, University of Cambridge
[name] (Co-investigator)	Research Director, Trauma Audit and Research Network (TARN)
[name] (Co-investigator)	Professor of Anaesthesia, University of Cambridge
[name] (Co-investigator)	Director, ICNARC
[name] (Co-investigator)	Consultant in Neuroanaesthesia and Neurocritical care, The National Hospital for Neurology and Neurosurgery

[name] (Co-investigator)	Consultant in Adult Critical Care, Queen's Medical Centre, Nottingham
[name] (Independent)	Clinical Research Registrar in Neurosurgery, Nuffield Department of Surgery, Oxford
[name] (Independent)	Consultant Anaesthetist, The Walton Centre for Neurosurgery, Liverpool
[name] (Service User Representative)	Headway UK, London
[name] (Study Coordinator)	RAIN Study Coordinator, ICNARC
(Research Fellow)	To be appointed

Study Management Group

The day-to-day running of the trial will be overseen by a Study Management Group consisting of the Chief Investigator and ICNARC-based Co-investigators, the Study Coordinator and the Research Fellow.

Data monitoring

As the study does not involve any change to usual care for patients, an independent Data Monitoring Committee (DMC) will not be required. The SSG will oversee those responsibilities usually delegated to a DMC and these have been incorporated into the terms of reference (Appendix 4).

Service user involvement

Through *Headway UK*, the national charity for people affected by brain injury, and their local Groups and Branches, a representative will be identified to take a full and active role in the SSG, promoting the patient's perspective. All involvement of service users in RAIN will follow the guidelines and recommendations for good practice from INVOLVE (<http://www.invo.org.uk>).

Research Governance

RAIN will be managed according to the Medical Research Council's Guidelines for Good Research Practice (http://www.mrc.ac.uk/pdf-good_research_practice.pdf), Guidelines for Good Clinical Practice in Clinical Trials (<http://www.mrc.ac.uk/pdf-ctg.pdf>) and Procedure for Inquiring into Allegations of Scientific Misconduct (http://www.mrc.ac.uk/pdf-mis_con.pdf). ICNARC has developed its own policies and procedures based on these MRC guidelines, which are adhered to for all research activities at ICNARC. In addition, ICNARC has contractual confidentiality agreements with all members of staff. Policies regarding alleged scientific misconduct and breach of confidentiality are reinforced by disciplinary procedures.

Ethical arrangements

Informed consent for inclusion in RAIN will be sought at the six-month follow-up. A patient information sheet and consent form will be included with the questionnaire. This will include contact details for the RAIN investigators, and the patient will be encouraged to contact the RAIN team if they have any questions. For patients unable to give their informed consent due to the nature of their head injury, the consent form may be completed by a consultee (as defined under the Mental Capacity Act 2005 and in compliance with the Adults with Incapacity (Scotland) Act 2000). Any patient, or the consultee, may withdraw their informed consent at any time without being required to give a reason. Applications to an NHS Research Ethics Committee and to the Patient Information Advisory Group (PIAG) under Section 251 of the NHS Act 2006 to hold patient identifiable data prior to consent are pending. The Case Mix Programme already holds PIAG approval to hold limited identifiable data (date of birth, sex, postcode, NHS number) – approval number PIAG 2-10(f)/2005.

Funding

Research costs for this study have been met by a grant from the National Institute for Health Research (NIHR) Health Technology Assessment (HTA) Programme (project reference 07/37/29). There are no NHS support costs or excess treatment costs associated with this research as there is no deviation from usual care.

Indemnity

[figure not shown]
ICNARC holds professional liability insurance (certificate number A05305/0808, Market International Insurance Co Ltd) to meet the potential legal liability of the sponsor for harm to participants arising from the management of the research. Indemnity to meet the potential legal liability of the sponsor and employers for harm to participants arising from the design of the research is provided by the NHS indemnity scheme. Indemnity to meet the potential legal liability of investigators/collaborators for harm to participants arising from the conduct of the research is provided by the NHS indemnity scheme or through professional indemnity.

REFERENCES

